**Inclusion criteria**

Patients must meet all the inclusion criteria below to be eligible for inclusion in the study:

1. IC1: Evidence of a personally signed and dated informed consent document indicating that the patient (or his/her legal representative) has been informed of all relevant aspects of the study. Informed consent will only be obtained from patients who are still alive.
2. IC2: Aged 18 or over.
3. IC3: Histologically confirmed diagnosis of advanced renal cell carcinoma, with at least one radiological evaluation of the disease according to RECIST 1.1 criteria.
4. IC4: Treatment with axitinib, as second-line or further line treatment and with progression-free survival PFS of 9 months or more or with disease progression at the first response assessment.

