**Analysis population****All analyses will be performed with evaluable patients.**

The CRF contains the information related to the eligibility criteria as binary variable (Yes/No) for each of the described items.

Several of these criteria can be verified with the data recorded in the CRF. This verification is performed in order to prevent the inclusion of non-evaluable participants in the statistical report and prior to the start of any analysis.

These patients will be considered screening failure, and in the statistical report they will thus be included in a table of patient disposition together with the patients screening failure initially confirmed by the sponsor.

The criteria to be verified in the patient CRFs to define the evaluable population are described below:

- An "evaluable" patient must have received at least one dose of axitinib prior to inclusion in the study: it must be verified that the "Starting dose" and the "Treatment start date with axitinib" have been specified in "Treatment with axitinib". This date must be prior to the date of signing the informed consent (for patients who are still alive at enrolment).

- Inclusion requirement *Patients must have received axitinib as second-line treatment or further line*: it must be verified that there is information concerning a first-line treatment in the "First-line treatment" section.

- IC1: *Evidence of a personally signed and dated informed consent document indicating that the patient (or his/her legal representative) has been informed of all relevant aspects of the study. Informed consent will only be obtained from patients who are still alive.*

It must be verified that the date of signing the informed consent is specified (for patients who are still alive at enrolment).

Noted that for patients already dead before the study inclusion, the CII could be "No".

- IC2: *Aged 18 or over.*

It must be verified that the age calculated with respect to the date of the baseline visit is  $\geq 18$  years.

- IC3: *Histologically confirmed diagnosis of advanced renal cell carcinoma, with at least one radiological evaluation of the disease according to RECIST 1.1 criteria.*

It must be verified that the following data have been indicated: Date of first diagnosis, Tumour stage at disease diagnosis, Date of advanced disease diagnosis, Stage of advanced disease, Metastasis location, Best treatment response (first-line treatment).

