 $(\text{Dose increase date or Dose reduction date} - \text{Start date of treatment with axitinib}) / 30.4375$
  - Duration (months) of subsequent treatments =  
 $(\text{Date of end of subsequent treatment or of latest follow-up if not suspended} - \text{Date of start of subsequent treatment}) / 30.4375$ . In the case of several subsequent treatments per patient, proceed as follows: the duration in months of each of the subsequent treatments will be calculated (from the start date to the end date or last check if it continues). This will be done for all subsequent treatments and then proceed to make the sum per patient of all durations of subsequent treatments

- Progression-Free Survival (PFS, in months) =  
 (Date of Disease Progression on treatment with axitinib or death from any cause – Date of start of treatment with axitinib) / 30.4375  
 If there is no progression or death, the case is censored as  
 PFS (months) = (Date of latest follow-up – Date of start of treatment with axitinib) / 30.4375
- Time to progression (TTP, in months) =  
 (Date of Disease Progression – Date of start of treatment with axitinib) / 30.4375  
 If there is no progression, the case is censored as  
 TTP (months) = (Date of latest follow-up – Date of start of treatment with axitinib) / 30.4375
- Overall Survival (OS, in months) = (Date of death – Date of start of treatment with axitinib) / 30.4375  
 If death has not occurred, the case is censored as  
 Overall Survival (OS, in months) = (Date of latest follow-up – Date of start of treatment with axitinib) / 30.4375
- Overall Survival since the start of first-line treatment (OS, in months) = (Date of death – Date of start of first-line treatment) / 30.4375  
 If death has not occurred, the case is censored as  
 Overall Survival (OS, in months) = (Date of latest follow-up – Start date of first treatment) / 30.4375
- Patient subgroups
  - A-Long-term responders: comprising patients with PFS  $\geq 9$  months.
  - B-Refractory (primary): comprising patients with best response to treatment = PD. This date is collected in the CRF form “axitinib treatment”.
- MSKCC risk group (described in appendix 11.1.). It will be analysed “Before the beginning of the first line”. These calculations will be performed on patients who have data on all the variables involved (in the case of a patient who does not have data on all the variables but has > 2 factors, it will be classified in the “Poor” risk group.

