It will be calculated as follows: Progression Free Survival to sunitinib (SLP, in months) = (Date of Progression of the Disease to treatment with sunitinib - Start date of treatment with sunitinib) / 30,4375. If there is no progression, the case is censored in SLP (months) = (Start date of treatment with axitinib - Start date of treatment with sunitinib) / 30,4375.

- **Majority sequence**

The number of patients receiving the second-line treatment will be shown, following the sequence that is most observed in all the patients included (SUT-AXI-NIVO).

The following analyzes will be carried out by group (long responders / refractories):

- Best treatment response (CR, PR, SD, DP).
- Duration of treatment (months).
- Progression-free survival. PFS will be shown in all patients with sunitinib-axitinib sequence and PFS per group.
- Objective response rate (ORR) and clinical benefit.
- Time to Progression
- Overall Survival. OS will be shown in all patients with sunitinib-axitinib sequence and OS per group
- Overall Survival since the beginning of 1st line. OS will be shown in all patients with sunitinib-axitinib sequence and OS per group

It is defined as: Global Survival from the beginning of the first line (SG, in months) = (Exit date - Start date of first line treatment) / 30,4375. If there is no exitus the case is censored in Global Survival (SG, in months) = (Date of last control - Start date of the first treatment) / 30,4375.

- To describe the duration of treatment with axitinib. It will be described as it is described in section 7. Definition of variables and objectives
- To describe the percentage of patients who had increase the dose of axitinib above 5 mg twice daily. It will be described as it is described in section 7. Definition of variables and objectives
- To describe the percentage of patients who had reduce the dose of axitinib below 5 mg twice daily. It will be described as it is described in section 7. Definition of variables and objectives
- To describe the tolerability of axitinib (see point 9.2. Statistical analyses, Safety objectives).
- To describe the response to treatments received at progression. The treatments received will be described in cases of DP for first-line, 2nd line, etc.; that is, in treatments prior to axitinib.
- Overall survival based on post treatment
  - o Overall survival. The OS will be displayed according to having received further treatment (Yes vs. No).

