**Inferential analysis:**

When an inferential analysis is required, parametric tests will be used for continuous variables, and non-parametric tests will be used for ordinal, categorical or non-parametric variables. The hypothesis tests to be carried out will be two-tailed test in all cases with a significance level of 0.05. For variables that are not adjusted to a normal (or parametric) distribution, the Mann–Whitney U test (for unpaired data) or the Wilcoxon signed-rank test (for paired data) will be used. The Chi-squared test (or Fisher’s exact test when applicable) shall be used for analysing the contingency tables and for the comparison of proportions and/or frequency distributions.

Survival analyses shall be performed using the Kaplan-Meier method, providing the median, mean, 95% confidence intervals, as well as number of events and number of censored cases.

When it is necessary to compare survival functions, the log-rank test will be used.

The assumptions of normality and homoscedasticity of the variables for the use of parametric tests will be studied.

The level of significance in all the statistical inference tests will be  $\alpha=0.05$ , two-tailed.

Adjustment by multiple comparisons is not planned.

Estimates will be calculated with a 95% confidence level, the SPSS statistical analysis software package, V18.0 or later, will be used.

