## 9.2 STATISTICAL ANALYSES

### Primary objective

A descriptive analysis will be performed of the baseline clinical characteristics (clinical history of renal cell carcinoma, first-line treatment, other treatments prior to axitinib) of the population of patients who are long-term responders with axitinib, in those patients refractories to treatment, and overall.

The baseline clinical characteristics will be statistically compared according to membership to each one of the two extreme treatment response groups.

Efficacy variables will be analyzed and compared between groups of long responders and refractory patients: PFS, time to progression, overall survival, overall survival from the beginning of the 1st line. These analyzes will be added in the statistical report in the sections in which these same analyzes are shown for the total N of patients.

In addition, the association of clinical factors of interest with the benefit of treatment will be analysed by logistic regression (see point 7.1. Primary objective).

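### Overall survival from first-line start counts guaranteed survival as time at risk: it is conditional survival, and its between-group log-rank test cannot be interpreted

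*SAP*

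**What the plan says.** SAP section 7 defines "Overall Survival since the start of first-line treatment (OS, in months") as the time from the first-line start date to death, divided by 30.4375. Patients still alive are censored at "Overall Survival (OS, in months) = (Date of latest follow-up – Start date of first treatment) / 30.4375". Neither formula has an entry time.

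Eligibility is set later in the patient's course. The SAP inclusion criteria require "Treatment with axitinib, as second-line or further line treatment and with progression-free survival PFS of 9 months or more", or else progression at the first response assessment. The analysis-population text adds that an evaluable patient "must have received at least one dose of axitinib prior to inclusion in the study".

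The variable is used in two places. SAP 9.2, under the primary objective, names "overall survival, overall survival from the beginning of the 1st line" among the efficacy variables to be compared between long responders and refractory patients. SAP 7.2, under the majority sequence, says of it that "OS will be shown in all patients with sunitinib-axitinib sequence and OS per group". On method, SAP 9.1 states "Survival analyses shall be performed using the Kaplan-Meier method" and names the log-rank test for comparing curves.

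Neither document mentions left truncation, delayed entry or a landmark. The limitations section of the protocol (8.9) deals only with patient numbers.

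**The concern.** No included patient can have died between first-line start and axitinib start. A long responder cannot have died in the first 9 months on axitinib either, and a refractory patient lived at least to the progression that qualified him or her. People who started first line and died before axitinib are never sampled. Ordinary Kaplan-Meier from first-line start nevertheless treats all this guaranteed time as time at risk.

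Two conclusions are at stake. A median labelled as overall survival from first line invites a reader to set it beside first-line or sequence survival figures, with which it is not comparable. And the log-rank test compares two groups that are defined by what happened after the clock started, each with a different guaranteed minimum.

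**Working it through.** The plan states no median, event count or power for this variable, so there is no figure to reproduce. Four checks follow.

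**1. Direction (no assumptions).** At each death time the Kaplan-Meier factor is 1 − d/n. The planned n includes patients who, at that time since first-line start, had not yet entered. Delayed entry leaves them out, so n* ≤ n. All deaths occur after entry, so d is unchanged. Hence 1 − d/n* ≤ 1 − d/n, and the planned curve and median are at or above their delayed-entry versions in each group. In 6,000 simulated group samples (sizes 40 and 20, median gap 11 months) the planned median was never lower. It was equal in 37, and the typical excess was 5.6 months (5th to 95th percentile 0.6 to 20.9).

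**2. Size among patients reaching axitinib (assumed model).** Survival from first-line start and the gap to axitinib are taken as independent exponentials. The upper inputs are stand-ins from the protocol: median survival 29 months (6.1.1) and first-line sunitinib PFS of 11 months (6.1.3). The lower inputs, 24 and 8 months, are assumptions. With a = ln 2/(median survival) and b = ln 2/(median gap), survival among those reaching axitinib is

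S(t) = [(a+b)e^(−at) − a·e^(−(a+b)t)]/b.

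- 29 and 11: a = 0.0239, b = 0.0630. At t = 41.6, (0.0869 × 0.370 − 0.0239 × 0.0269)/0.0630 = 0.50.
- 24 and 8: a = 0.0289, b = 0.0866. At t = 33.5, (0.1155 × 0.380 − 0.0289 × 0.0209)/0.0866 = 0.50.

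The planned median is thus 33.5 to 41.6 months where the model sets that of all starters at 24 to 29. A second model (check 3), with gaps of 6 to 24 months and 10% to 50% dying before axitinib, puts the excess over all starters at about 2 to 14 months.

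**3. The groups actually analysed (assumed model).** Axitinib PFS is exponential with median 6.7 months, and post-progression survival is exponential with mean 14.53 months, which gives median survival of 20.1 months (both medians from Protocol 6.1.6). The gap is exponential. Long responders have PFS ≥9 months and refractory patients PFS ≤3 months. Medians in months from first-line start:

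| Median gap | Long: planned | Long: entry at axitinib | Long: entry at axitinib + 9 | Refractory: planned | Refractory: entry at axitinib |
|---|---|---|---|---|---|
| 6 | 38.1 | 37.0 | 34.0 | 20.7 | 14.2 |
| 11 | 44.5 | 40.3 | 35.3 | 26.9 | 14.6 |
| 24 | 58.9 | 44.0 | 36.5 | 41.4 | 14.6 |

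If refractory patients enter at progression, the hazard is constant at 1/14.53, so the median is 14.53 × ln 2 = 10.1 for any gap.

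**4. The contrast.** Each group's median depends only on its own gap, so rows can be combined.

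- Same gap (11) in both groups: planned 44.5 − 26.9 = 17.6; entry at axitinib 40.3 − 14.6 = 25.7; both groups entering at eligibility 35.3 − 10.1 = 25.2. The planned analysis narrows the difference.
- Gap 24 in long responders and 6 in refractory patients: planned 58.9 − 20.7 = 38.2; entry at axitinib 44.0 − 14.2 = 29.8; entry at eligibility 36.5 − 10.1 = 26.4. The planned analysis widens it.

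Unequal gaps are plausible here, since SAP 7.1 lists first-line duration as a candidate factor for response.

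**The case against.** The strongest reply is that the SAP nowhere presents this variable as survival of everyone who started first line. A treatment sequence contains by definition only patients who received both drugs, and total survival among them is a legitimate conditional description. That stands; what is missing is the label and the limitation. It also stands that the study is exploratory, that the variable is no stated objective, and that the logistic model of factors does not use it.

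Three stronger readings are tempting and are not supported.

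- A reader might infer that every median exceeds that of the wider first-line population. It need not: at a gap of 11 months the refractory median is 26.9, against 28.2 to 33.2 for all starters when 30% to 10% die before axitinib. That group is selected for early progression.
- A reader might infer that the group difference is inflated. Check 4 shows it can be narrowed or widened.
- A reader might take 41.6 against 29 months as the size of the bias. It is the upper end of a range built on stand-ins, and a PFS median is not a time to axitinib.

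Delayed entry is not a full cure either. It assumes entry time is independent of survival, while Protocol 6.1.6 reports a non-significant tendency to longer survival after longer prior sunitinib. It does not undo grouping by outcome, and can fall below the value for all starters (26.4 against 28.2 months for all patients reaching axitinib, at a gap of 11 and 30% dying first). With about 20 refractory patients (60 at 2:1) and entry at axitinib start, the simulated curve reached zero before the last death in about 26% of samples, and its median ranged from about 4 to 24 months (5th to 95th percentile).

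**Conclusion.** The point holds. It follows from the documents alone that each planned median is at or above its own delayed-entry counterpart, and that the figure is not overall survival of first-line or sequence starters. The size cannot be fixed: 33.5 to 41.6 months among those reaching axitinib rests on independent exponentials with assumed medians, because the gap is not given. The between-group log-rank test is not interpretable, since grouping follows the time origin and guaranteed survival differs between groups; no direction of bias in that contrast can be claimed. The analysis of factors associated with long response is untouched, so this should be corrected but does not threaten the main result.

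**What to change.** - In SAP 9.2, remove survival from first-line start from the variables compared between groups, so that no log-rank test is run on it.
- In SAP 7 and 7.2, either delete the variable or keep it as a description only, titled *survival from first-line start, conditional on reaching axitinib and being in an extreme-response group*. State the limitation and make no comparison with first-line overall survival.
- If an estimate adjusted for truncation is wanted, add a sensitivity analysis with delayed entry at the date each patient became eligible: axitinib start plus 9 months for long responders, and the date of first-assessment progression for refractory patients. Report the risk-set sizes and the assumption that entry time is independent of survival.

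The first two changes cost only SAP wording and lose no stated objective. The third uses dates already in the CRF but needs a routine that accepts entry times, and early risk sets will be small, above all among refractory patients.

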Risk groups are defined considering the following five factors (Favourable, Intermediate, Poor):

- ECOG/PS <1 (related to KPS <80)
- Time from first Diagnosis to Systemic Treatment less than 1 year
- LDH >1.5 x ULN
- Corrected calcium >10 mg/dl
- Haemoglobin < LLN

---

The risk groups are as follows:

- Favourable: 0 factors
  - Intermediate: 1 or 2 factors
  - Poor: >2 factors
- 
- Heng (or IMDC) risk group (described in appendix 11.1.). It will be analysed “at the beginning of the axitinib treatment” and “on the axitinib discontinuation”. These calculations will be performed on patients who have data on all the variables involved (in the case of a patient who does not have data on all the variables but has > 2 factors, it will be classified in the “Poor” risk group.

Risk groups are defined taking into account the following six factors (Low, Intermediate, High):

- ECOG/PS <1 (related to KPS <80)
- Time from first Diagnosis to Systemic Treatment less than 1 year
- Corrected calcium >10 mg/dl
- Haemoglobin < LLN
- Neutrophils > ULN
- Platelets > ULN

The risk groups are as follows:

- Favourable: 0 factors
  - Intermediate: 1 or 2 factors
  - Poor: >2 factors
- 
- Risk group according to MSKCC Criteria for patients previously treated with a TKI (defined in appendix 11.1). It will be analysed “at the beginning of the axitinib treatment”. Of note, all patients must have been previously treated with a TKI. These calculations will be performed on patients who have data on all the variables involved (in the case of a patient who does not have data on all the variables but has > 2 factors, it will be classified in the “Poor” risk group.

Risk groups are defined taking into account the following three factors (Low, Intermediate, High):

- ECOG/PS <1 (related to KPS <80)
- Haemoglobin < LLN
- Corrected calcium >10 mg/dl

The risk groups are as follows:

- Favourable: 0 factors
- Intermediate: 1 factor
- Poor: 2 or 3 factors
- The Objective Response Rate (ORR) is the frequency of subjects with CR or PR.
- The Clinical Benefit Rate is the frequency of subjects with CR, PR or SD.
- Increase of the axitinib dose to above 5 mg twice daily. Defined as having specified "Increase" at least one time, and in this case having specified "New dose" >5 mg/12h.
- Reduction of the axitinib dose to below 5 mg twice daily. Defined as having specified "Reduction" at least one time, and in this case having specified "New dose" <5 mg/12h.

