## 7.1 PRIMARY OBJECTIVE

In order to meet the study's primary objective, the baseline clinical characteristics of two patient groups with extreme response to the drug will be compared: A group of patients with long-term responses to the drug (long-term responders to axitinib) versus a group of patients with disease progression at the first assessment after the initiation of treatment (group of patients refractory to axitinib).

The classification (in long-term responders or refractory patients) will be based on PFS (in months), as indicated in section 5.2.

It will be shown the following descriptive tables:

- “Long responder” patient (Yes, No). “Long responding patient” is defined if he / she has an PFS  $\geq 9$  months (during axitinib treatment). The 95% CI will be displayed.
- PFS in long responding patients. Only the descriptive analysis of the time in months and the CI for the average, will be shown.
- “Refractory” patient (Yes, No). "Refractory patient" is defined if there is a better response to treatment = PE (to axitinib treatment). 95% CI will be shown.
- PFS in refractory patients. Only the descriptive analysis of the time in months and the CI for the average will be shown.
- Patient group (Long respondent, refractory). It is defined in section 5.2. IC95% will be displayed

At the same time, In addition to comparisons of baseline clinical characteristics between the groups (long-term responders, refractory patients), an association analysis of the following factors with the study groups will be performed:

- Age with respect to first visit ( $\leq 65$  years and  $> 65$  years).
- Age with respect to first diagnosis ( $\leq 65$  years and  $> 65$  years).
- Age with respect to start of axitinib ( $\leq 65$  years and  $> 65$  years).
- Baseline ECOG/PS and at the initiation of first line treatment (0, 1 and  $\geq 2$ ).
- Baseline ECOG/PS and at the initiation axitinib treatment (0, 1 and  $\geq 2$ ).
- Baseline ECOG/PS and at the end of axitinib treatment (0, 1 and  $\geq 2$ ).
- Number of previous treatment lines
- Number of previous treatment lines (1, 2 and  $\geq 3$ )
- Previous nephrectomy (yes and no)
- MSKCC (or IMDC) risk group in all moments in which it is analysed during the study (favourable, intermediate and poor)

- Histology (100% clear cells, primarily clear cells, primarily non-clear cells, 100% non-clear cells)
- Duration of first-line treatment

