## 11 APPENDICES

### 11.1 APPENDIX 1: RISK GROUPS

#### A1.1 MSKCC risk group

Risk factors are defined to establish the patient's prognostic group at the initiation of mRCC treatment as follows.

Extract from Motzer et al. *Interferon-Alfa as a Comparative Treatment for Clinical Trials of New Therapies Against Advanced Renal Cell Carcinoma*. JCO 2001. Vol 20. No1. (JHJanuary 1 (2002) pp 289-296.

*“The Memorial Sloan–Kettering Cancer Center (MSKCC; NY, USA) criteria, first published in 1999, defined pretreatment clinical features that were predictive of survival in untreated patients with mRCC who were going to receive cytokine therapy, particularly IFN- $\alpha$ . The MSKCC risk system stratifies patients with mRCC into poor-, intermediate- and favorable-risk categories based on the number of adverse clinical and laboratory parameters present. Poor prognostic factors include a Karnofsky performance status (KPS) of less than 80, time from diagnosis to treatment less than 12 months, serum lactate dehydrogenase (LDH) more than 1.5-times the upper limit of normal (ULN), corrected serum calcium >10.0 mg/dl and hemoglobin less than the lower limit of normal (LLN).[21] Patients in the **favorable-risk** group have no poor prognostic factors, those in the **intermediate-risk** category have one or two adverse prognostic factors, and patients with **poor-risk** RCC have more than two poor prognostic factors.”*

Table 6. Results of Multivariate Analysis

	Parameter Estimate	SE	$\chi^2$	P	Risk Ratio	95% CI
Lactate dehydrogenase	1.1715	0.1734	45.65	.0001	3.23	2.30-4.53
Hemoglobin	0.4232	0.1053	16.14	.0001	1.53	1.24-1.88
Corrected calcium	0.6561	0.1459	20.23	.0001	1.93	1.45-2.57
Karnofsky performance status	0.4153	0.1283	10.48	.0012	1.52	1.18-1.95
Interval from initial RCC diagnosis to IFN- $\alpha$ treatment*	0.3914	0.1184	10.93	.0009	1.48	1.17-1.87

\*Less than 1 year versus  $\geq$  1 year.

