#### A1.2 Heng risk group

Risk factors are defined to establish the patient's prognostic group at the initiation of mRCC treatment, in accordance with the Heng classification, as follows.

Extract from Heng et al. *Prognostic factors for overall survival in patients with metastatic renal cell carcinoma treated with vascular endothelial growth factor-targeted agents: results from a large, multicenter study*. J Clin Oncol. 2009 Dec 1;27(34):5794-9

*“A multivariate analysis identified a Karnofsky-PS score of <80 at the initiation of treatment, the period from the RCC diagnosis to metastasis treatment of <1 year, anemia, hypercalcemia (corrected Ca > 10), neutrophilia and thrombocythemia as independent poor prognostic factors. Patients were classified into a **favorable-prognosis** group (with 0 poor prognostic factors), **intermediate-prognosis** group*

(with 1–2 poor prognostic factors) and **poor-prognosis** group (with 3–6 poor prognostic factors).”

Parameter	Parameter Estimate $\pm$ SE	Hazard Ratio	95% CI	P
Clinical				
KPS < 80%	0.92 $\pm$ 0.14	2.51	1.92 to 3.29	< .0001
Time from diagnosis to treatment < 1 year	0.35 $\pm$ 0.13	1.42	1.09 to 1.84	.0098
Laboratory				
Hemoglobin < LLN	0.54 $\pm$ 0.14	1.72	1.31 to 2.26	.0001
Calcium > ULN	0.59 $\pm$ 0.17	1.81	1.29 to 2.53	.0006
Neutrophil count > ULN	0.88 $\pm$ 0.17	2.42	1.72 to 3.39	< .0001
Platelet count > ULN	0.40 $\pm$ 0.16	1.49	1.09 to 2.03	.0121

NOTE. Total number of patients = 564.  
Abbreviations: SE, standard error; KPS, Karnofsky performance status; LLN, lower limit of normal; ULN, upper limit of normal.

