Low Karnofsky performance status (< 80%), low serum hemoglobin, and high corrected calcium were identified as risk factors. Corrected calcium and hemoglobin were dichotomized using previously defined cut-points (corrected calcium, < 10 v ≥ 10 mg/dL; hemoglobin, ≤ 13 v > 13 g/dL for males and ≤ 11.5 v > 11.5 g/dL for females [45]), and the univariate association of these dichotomized variables with survival is given in the right side of Table 4. A multivariate Cox model was then fit using the categoric forms of the variables (Table 5). Each patient was then assigned to one of three risk groups: those with zero risk factors (**favorable risk**), those with one risk factor (**intermediate risk**), and those with two or three risk factors (**poor risk**).”

Parameter	Parameter Estimate	SE	$\chi^2$	P	Risk Ratio	95% CI
KPS	1.26	0.26	23.4	< .001	3.5	2.1 to 5.9
Corrected calcium	1.21	0.28	18.7	< .001	3.4	1.9 to 5.8
Hemoglobin	0.50	0.21	5.5	.02	1.7	1.1 to 2.5

  

No. of Risk Factors	No. of Patients* (%)	No. of Patients Alive	Median Survival (months)	95% CI	1-Year Survival	3-Year Survival
0	56 (42)	13	22.1	17.7 to 26.3	76%	25%
1	46 (35)	8	11.9	8.3 to 16.2	49%	11%
2 or 3	30 (23)	3	5.4	4.8 to 6.5	11%	0%

NOTE. Analysis performed for patients enrolled after 1/1/1990.  
 Abbreviation: KPS, Karnofsky performance status.  
 \*Five patients are missing data on one of the risk factors.

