### 11.2 APPENDIX 2: RELATIONSHIP BETWEEN KPS AND ECOG.

KPS is not recorded in the CRF, but it is related to ECOG in line with the following table.

KPS	ECOG
100 - 90	0
80 - 70	1
60 - 50	2
40 - 30	3
20 - 10	4

This table is an adaptation of that which appears in:

<http://oncologypro.esmo.org/Oncology-in-Practice/Practice-Tools/Performance-Scales>

Moreover, which is based on that published in Am J Clin. Oncol.: Oken, M.M., Creech, R.H., Tormey, D.C., Horton, J., Davis, T.E., McFadden, E.T., Carbone, P.P.: Toxicity And Response Criteria Of The Eastern Cooperative Oncology Group. Am J Clin Oncol 5:649-655, 1982. The Eastern Cooperative Oncology Group, Robert Comis M.D., Group Chair.

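### All three risk scores count ECOG 0, the best performance status, as the adverse factor; the sign is reversed and the handling of ECOG 1 is not stated

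*SAP*

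**What the plan says.** SAP section 7 defines three risk scores: the five-factor MSKCC score, analysed before the first line; the six-factor IMDC score, analysed at axitinib start and at discontinuation; and a three-factor MSKCC score for patients previously treated with a TKI, analysed at axitinib start. Each list of adverse factors contains the same entry, "ECOG/PS <1 (related to KPS <80".

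The definitions refer to Appendix 1: "MSKCC risk group (described in appendix 11.1" for the five-factor score and "Risk group according to MSKCC Criteria for patients previously treated with a TKI (defined in appendix 11.1" for the three-factor score. The appendix extracts give the performance-status factor as follows.

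- A1.1 (MSKCC): "Poor prognostic factors include a Karnofsky performance status (KPS) of less than 80".
- A1.2 (IMDC): "A multivariate analysis identified a Karnofsky-PS score of <80 at the initiation of treatment".
- A1.3 (MSKCC, second line): "Low Karnofsky performance status (< 80%), low serum hemoglobin, and high corrected calcium were identified as risk factors".

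Appendix 2 supplies the only conversion: "KPS is not recorded in the CRF, but it is related to ECOG in line with the following table". Its rows are ECOG 0 = KPS 100–90, ECOG 1 = 80–70, ECOG 2 = 60–50, ECOG 3 = 40–30 and ECOG 4 = 20–10.

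SAP 7.1 names as a factor of the primary objective "MSKCC (or IMDC) risk group in all moments in which it is analysed during the study". Pre-axitinib factors with P<0.15 go forward to the logistic model. SAP 7.2 restricts the subpopulation of special interest to patients whose MSKCC group at axitinib start is favourable or intermediate. By section 7, that is the three-factor score.

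**The concern.** Higher ECOG is worse, so a factor that marks poor performance status must take the high ECOG grades. The printed condition takes the lowest grade. Fit patients gain an adverse point and unfit patients lose one, which pushes both towards the wrong group.

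Correcting the direction does not complete the rule. The ECOG 1 row covers KPS 80 and 70, one on each side of the cut-off, and nothing in the SAP says whether ECOG 1 counts. Two programmers could each repair the sign and still classify every ECOG 1 patient differently.

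At stake are the risk-group rows of the primary comparison between long-term responders and refractory patients, the risk-group candidates for the logistic model, and membership of the SAP 7.2 subpopulation.

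**Working it through.** **1. The stated equivalence.** Applying Appendix 2 to each possible rule:

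| Rule | KPS covered | Part of KPS <80 missed | KPS ≥80 wrongly included |
|---|---|---|---|
| ECOG <1 (printed) | 90, 100 | all (10–70) | 90, 100 |
| ECOG ≥2 | 10–60 | 70 | none |
| ECOG ≥1 | 10–80 | none | 80 |

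The printed equivalence does not reproduce: its overlap with KPS <80 is empty. No whole-number ECOG cut-off matches KPS <80 exactly.

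**2. Factor profiles that change group.** Let k be the number of other adverse factors present. One factor more or less changes the group when k is 0 or 2 in the MSKCC and IMDC scores (0 / 1–2 / >2), and when k is 0 or 1 in the three-factor score (0 / 1 / 2–3). Against ECOG ≥2 the rule differs at two ECOG levels (0 and ≥2). Against ECOG ≥1 it differs at all three (0, 1, ≥2).

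- Three-factor, two other factors: 1 + 2 = 3 combinations. Changed: 3×2 = 6, or 3×3 = 9, of 3×4 = 12.
- MSKCC, four other factors: 1 + 6 = 7. Changed: 14 or 21 of 3×16 = 48.
- IMDC, five other factors: 1 + 10 = 11. Changed: 22 or 33 of 3×32 = 96.

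Every shift is one category.

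**3. The SAP 7.2 filter (three-factor, Poor versus not).** The boundary is crossed when k = 1, which is two combinations. Against ECOG ≥2, two ECOG 0 profiles are wrongly excluded and two ECOG ≥2 profiles wrongly included: 4 of 12. Against ECOG ≥1, two are wrongly excluded and four wrongly included: 6 of 12.

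**4. Share of patients (illustration).** The documents give no prevalences. Assumed, with factors independent: ECOG 0/1/≥2 = 40/45/15%, low haemoglobin 45%, high calcium 10%, high LDH 15%, under one year from diagnosis to treatment 45%, high neutrophils 15%, high platelets 15%.

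Three-factor score: P(k=0) = 0.55×0.90 = 0.495 and P(k=1) = 0.45×0.90 + 0.55×0.10 = 0.460, together 0.955. Against ECOG ≥2 the share is (0.40 + 0.15)×0.955 = 52.5%; against ECOG ≥1 it is 95.5%. The other scores follow in the same way from P(k=0) + P(k=2). Ranges take every corner of haemoglobin 30–60%, calcium 5–20%, LDH 10–30%, under one year 30–60%, neutrophils and platelets 10–25%, with ECOG mixes 40/45/15, 55/40/5 and 30/50/20.

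| Score | Against ECOG ≥2 | Against ECOG ≥1 |
|---|---|---|
| Three-factor | 53% (44–59%) | 96% (88–99%) |
| MSKCC | 27% (24–33%) | 50% (47–56%) |
| IMDC | 27% (23–33%) | 49% (45–54%) |

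**5. Effect on the association (illustration).** Take the log-odds of being refractory as linear in the true three factors, with the intercept set so that one third are refractory (the protocol's 2:1 ratio). Compare Poor with the rest at the base prevalences.

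| Weights | True factor | OR, true score | OR, printed rule |
|---|---|---|---|
| ln 2 each | ECOG ≥2 | 2.82 | 1.56 |
| ln 2 each | ECOG ≥1 | 2.53 | 1.12 |
| 1.26, 1.21, 0.50 | ECOG ≥2 | 4.27 | 1.43 |
| 1.26, 1.21, 0.50 | ECOG ≥1 | 3.12 | 0.81 |

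The second set is the A1.3 survival coefficients for KPS, calcium and haemoglobin, borrowed here as log-odds. Over the three ECOG mixes, the last odds ratio stays at 0.81–0.85.

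**The case against.** The strongest reply is that this is a typing slip that the SAP itself resolves. The same line says KPS below 80, the definitions point to Appendix 1, and all three extracts give the right direction. A statistician following those references would not code ECOG 0 as adverse, and three identical lines may be one error pasted twice. Changing one character gives ECOG >1, which includes no patient with KPS 80 or above and misses only KPS 70. The largest figures (96% reclassified, odds ratio 0.81) need the other correction, ECOG ≥1. Under ECOG ≥2 the printed-rule odds ratio stays between 1.4 and 1.7 across both weightings and the three ECOG mixes, with no reversal.

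It is also fair that no harm is shown. The programming is not visible. SAP section 6 lists ECOG/PS as Yes/No/Unknown; if sites ticked an adverse criterion directly, the printed threshold may not drive the derivation. The profile counts weight rare and common profiles alike. The study is exploratory, with about 60 patients, and risk group is one factor among many.

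Most of this limits reach and size, and it stands as such. It does not make the rule correct. The direction can be recovered, but no document states that ECOG ≥2 is the intended cut-off, and the ECOG 1 band still straddles 80. A PDF reading error cannot be fully excluded. It is unlikely, because the line appears three times and the neighbouring inequalities point the expected way, and it would leave the ECOG 1 question open.

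**Conclusion.** The concern holds. As printed, the performance-status factor in all three scores selects the patients it should spare, contradicting its own parenthesis and both appendices, and nothing elsewhere corrects it. The contradiction and the profile counts need no assumption about patients. The patient shares and odds ratios rest on assumed prevalences, independence and weights, and apply only if ECOG grades were recorded and the rule was programmed as printed. In that case the association of risk group with response would usually be weakened, and under some weights reversed.

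The reach is bounded. The definitions of the two response groups, the separate ECOG (0, 1, ≥2) and laboratory-factor analyses, and the full-set survival endpoints do not use this line. IMDC at discontinuation is not a baseline factor and cannot enter the model. The correction is nonetheless required, because the line defines a named variable of the primary objective and the filter for the SAP 7.2 subpopulation. The current SAP version was revised after draft results and still carries it.

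**What to change.** 1. Reverse the sign in the three definitions in SAP section 7, so that poor performance status is the adverse factor.
2. Add one sentence on how ECOG 1 counts. Neither ECOG ≥2 nor ECOG ≥1 equals KPS <80, so choose one as the main rule, give the reason, and show the other in a single sensitivity table.
3. Check the derivation code. If the printed rule was used, re-derive the risk-group tables, the logistic-model candidates and the SAP 7.2 subpopulation.
4. As a secondary check, confirm that ECOG grades, and not only Yes/No, were recorded at first-line start, axitinib start and discontinuation. The Yes/No/Unknown entry in SAP section 6 may be shorthand, but protocol 7.1 and SAP 7.1 need grades 0, 1 and ≥2.

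The cost is three corrected lines, one sentence, a code check and one extra table, plus a re-run of derived variables only if the printed rule was programmed. No new data are needed if grades are in the database.
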